This is an open trial pilot intervention study that involves: interviews, online surveys, online group video-conferencing intervention sessions, audio-recording of intervention sessions. The intervention will consist of 10 weekly 90-minute group supportive therapy sessions conducted via Zoom. Study outcomes will be both quantitative (surveys) and qualitative (interviews) in nature.

Study Duration

The entire study, including data analysis, is expected to last from August 2021 until August 2022. Participation for the subjects will begin in August 2021 (i.e., recruitment, pre-intervention assessment). Participants in the first group will begin the 10-week intervention in September-November 2021 and complete their post-intervention assessment in December 2021-January 2022. Participants in the second group will begin the 10-week intervention in February 2022 and complete their post-intervention assessment in May 2021-June 2022. Data analysis is expected to continue through August 2022.

Outcome Variables

Primary Objective:

- Acceptability:
 - *Main outcome*: Client Satisfaction Questionnaire-8 (CSQ-8)
 - Supportive variables: Treatment Expectations, Top Problems Assessment, Top Problems Tracking Form, Acceptability of Session Questionnaire, AFFIRM Acceptability Survey, Exit Interview-Acceptability of program format, delivery, and content
- Feasibility:
 - *Main outcome*: Session Attendance
 - Supportive variables: Homework Compliance Scale, Feasibility of Session Questionnaire, Feasibility of Program Questionnaire, Exit Interview-Program feasibility
- Need for refinement:
 - Main outcome: Exit interview
 - Supportive variables: Session Refinement Questions, Program Refinement Questions

Secondary Objective:

- Mental health:
 - Main outcome: Revised Children's Anxiety and Depression Scale (RCADS)
 - Supportive variables: Depressive Symptom Index Suicidality Subscale (DSI-SS), Strengths and Difficulties Questionnaire (SDQ), WHO-5 Well-Being Index
- Minority stress reactions:
 - Main outcome: Gender Minority Stress and Resilience Scale for Adolescents (GMSR-A) — Internalized Trans/Homophobia subscale
 - Supportive/related variables: Rest of GMSR-A, Child Perceived Discrimination Questionnaire (CPDQ), Outness Inventory (OI), Lesbian, Gay, Bisexual Affiliate Stigma Measure (LGB-ASM), Parental Rejection/Acceptance of LGBTQ child
- Emotion regulation & coping:
 - Main outcome: Children's Emotion Management Scales (CEMS)

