4.2 Outcome Variables/Endpoints

The following are the outcome variables and associated measures that will be administered at each time point (i.e., screening, pre-intervention, weekly assessments, and post-intervention) in the study:

* = Main outcome variable; all others are supportive variables

Screening:

 Mental health: Revised Children's Anxiety and Depression Scale (RCADS)*, Kiddie Schedule for Affective Disorders and Schizophrenia (K-SADS), Depressive Symptom Index - Suicidality Subscale (DSI-SS), Youth Psychosis At-Risk Questionnaire - Brief (YPARQ-B), Brief Child Mania Rating Scale - Parent Version (CMRS-P), Child & Adolescent Intellectual Disability Screening Questionnaire (CAIDS-Q)

Pre-intervention:

- Acceptability: Treatment Expectations
- Mental health: Revised Children's Anxiety and Depression Scale (RCADS)*, Depressive Symptom Index - Suicidality Subscale (DSI-SS), Strengths and Difficulties Questionnaire (SDQ), WHO-5 Well-Being Index, CRAFFT 2.1, Autism Quotient-10 (AQ-10)
- Minority stress reactions: Gender Minority Stress and Resilience Scale for Adolescents (GMSR-A)*, Outness Inventory (OI)
- Stigma exposure: Gender Minority Stress and Resilience Scale for Adolescents (GMSR-A), Child Perceived Discrimination Questionnaire (CPDQ), Lesbian, Gay, Bisexual Affiliate Stigma Measure (LGB-ASM), Parental Rejection/Acceptance of LGBTQ child
- Emotion regulation & coping: Children's Emotion Management Scales (CEMS)*, Emotion Regulation Questionnaire (ERQ-CA), Child Avoidance Measure (CAMS/CAMP), Children's Automatic Thoughts Scale - N/P version (CATS), Coping with Sexual Orientation-Related Minority Stress

Weekly:

- Acceptability: Top Problems Assessment (Session 1 only), Top Problems Tracking Form, Client Satisfaction Questionnaire-8 (Session 5 only)*, Acceptability of Session Questionnaire
- Feasibility: Session Attendance*, Homework Compliance Scale, Feasibility of Session Questionnaire
- Need for refinement: Session Refinement Questions
- Mental health: Revised Children's Anxiety and Depression Scale (RCADS-Short form)*, Depressive Symptom Index Suicidality Subscale (DSI-SS)

Post-intervention:

- Acceptability: Top Problems Tracking Form, Client Satisfaction Questionnaire-8 (CSQ-8)*, AFFIRM Acceptability Survey, Exit Interview-Acceptability of program format, delivery, and content

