- Feasibility: Feasibility of Program Questionnaire, Exit Interview-Program feasibility
- Need for refinement: Program Refinement Questions, Exit Interview-Program need for refinement*
- Mental health: Revised Children's Anxiety and Depression Scale (RCADS)*, Depressive Symptom Index - Suicidality Subscale (DSI-SS), Strengths and Difficulties Questionnaire (SDQ), WHO-5 Well-Being Index, CRAFFT 2.1
- Minority stress reactions: Gender Minority Stress and Resilience Scale for Adolescents (GMSR-A)*, Outness Inventory (OI)
- Stigma exposure: Gender Minority Stress and Resilience Scale for Adolescents (GMSR-A), Child Perceived Discrimination Questionnaire (CPDQ), Lesbian, Gay, Bisexual Affiliate Stigma Measure (LGB-ASM), Parental Rejection/Acceptance of LGBTQ child
- Emotion regulation & coping: Children's Emotion Management Scales (CEMS)*, Emotion Regulation Questionnaire (ERQ-CA), Child Avoidance Measure (CAMS/CAMP), Children's Automatic Thoughts Scale - N/P version (CATS), Coping with Sexual Orientation-Related Minority Stress, Multidimensional Scale of Perceived Social Support (MSPSS)

See Sections 4.2.1 and 4.2.2. for further explanations of each measure.

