- Kiddie Schedule for Affective Disorders and Schizophrenia (K-SADS). The KSADS (Kaufman et al., 1997, 2016) is a well-validated semi-structured diagnostic interview designed to identify DSM-5 mental disorders in youth. It has demonstrated excellent test-retest reliability in prior work (κ¬=0.77-1.00; Kaufman et al., 1997). The KSADS will be used in this study to determine whether youth are eligible for the study (inclusion: meet criteria for a DSM-5 internalizing disorder; exclusion: meet criteria for psychotic or bipolar spectrum diagnosis, active suicidality and/or homicidality, significant cognitive impairment, significant developmental or behavior disorder (if impairing youth's ability to participate in group therapy)
- Depressive Symptom Index Suicidality Subscale (DSI-SS). The DSI-SS (Joiner, Pfaff, & Acres, 2002; Metalsky & Joiner, 1997) is a 4-item self-report questionnaire that assesses the frequency and intensity of suicidality in the past two weeks. Items are scored on a 0-3 scale, where higher scores indicate more suicidal thoughts and impulses. Previous studies with the DSI-SS have revealed strong internal consistency (α = 0.90; Joiner, Pfaff, & Acres, 2002).
- Strengths and Difficulties Questionnaire (SDQ). The SDQ (Goodman, 1997; Goodman et al., 1998) is a 25-item questionnaire that assesses a broad range of psychological attributes of youth aged 3-17 years. Both the parent-report and the adolescent self-report versions of this scale will be used in this study. The measure

consists of five, five-item subscales measuring emotional difficulties, conduct problems, hyperactivity/inattention, peer relationship problems, and prosocial behavior. Participants are asked to rate whether each item is not true, somewhat true, or certainly true for them over the past six months. Previous studies with the SDQ have revealed good internal consistency ($\alpha = 0.73$; Goodman, 2001).

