- WHO-5 Well-Being Index (WHO-5). The WHO-5 (Psychiatric Research Unit, 1998) is a brief, 5-item self-report questionnaire that measures subjective well-being. It is derived from longer, 10- and 28-item versions of the same scale (Bech et al., 1996). Participants are asked to rate how well each of the items applies to them over the past 14 days on a scale from 0 = none of the time to 5 = all of the time. It has been widely used and deemed valid in a range of countries and contexts (Topp et al., 2015), and in youth as young as 9 years. The WHO-5 has demonstrated good internal consistency in adolescent samples (α = 0.82; de Wit et al., 2007).
- CRAFFT 2.1. The CRAFFT 2.1 (The Center for Adolescent Behavioral Health Research, 2020) is a 9-item youth-report screening tool for risky substance use in 12-21 year olds. Participants are asked to report on the frequency (# of days) of alcohol, marijuana, and other substance use in the past year, as well as high-risk behaviors (e.g., riding in a car driven by someone under the influence, use of substances to relax). Prior research indicates that the CRAFFT has good sensitivity in identifying both alcohol (0.79) and drug use (0.86) in adolescents (The Center for Adolescent Behavioral Health Research, 2020), and good predictive validity (Shenoi et al., 2019).
- Youth Psychosis At-Risk Questionnaire Brief (YPARQ-B). The YPARQ-B (Ord et al., 2004) is a 28-item youth-report questionnaire that assesses psychotic symptoms in adolescents as young as 12. It is an abbreviated version of the original 92-item scale by the same name (Ord et al., 2004). Participants are asked to indicate whether each item applies to them ("yes") or not ("no"), or if they are "undecided." The YPARQ-B has shown strong internal consistency in prior studies (α = 0.94; Fonseca-Pedrero et al., 2017), and high sensitivity (1.00) and specificity (0.80) (Kline et al., 2015). In this project, the YPARQ-B will be used to determine eligibility. Potential participants will be deemed ineligible if their score is 13 or above.

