If the parent/caregiver provides informed consent and parental permission for the screening process, they will then be asked to provide information about their child to assess eligibility, including the child's age, pertinent demographics, residency in New York, New Jersey, or Connecticut, availability to participate in study procedures, and mental health symptoms. If the parent/caregiver's responses to screening questions suggest their child is NOT eligible for the study, they will be thanked for their time and the survey will discontinue. If the parent/caregiver's responses to screening questions suggest their child may be eligible for the study, they will be asked to provide both their own contact information (name, email address, phone number, physical address), as well as contact information for their child. The parent/caregiver will be directed to a separate online survey to provide this contact information for themselves and their child. A link to the youth version of the screening survey will be subsequently emailed to the youth.

When the youth navigates to the screening survey, they will view an assent form for the screening process (details provided in section 5.5). If youth provide informed assent, they will be asked to complete questions to assess eligibility, including their LGBTQ status, pertinent demographics, availability to participate in study procedures, and mental health symptoms. Once youth complete this survey, they will be informed that based on their survey responses either 1) they are ineligible for the study, or 2) they may be eligible for the study, pending a phone screen with a study team member.

Study team members will review responses to the screening survey to identify potentially eligible participants. If a youth appears to meet study criteria (as documented in Section 5.3), including mental health symptoms on the RCADS-P or -C with a T-score of 65 or more (suggesting they likely meet diagnostic criteria for a DSM-5 internalizing disorder), the study team member will reach out to the child and their parent (by phone and/or email) to schedule a one-hour call (Zoom or phone) for a brief diagnostic interview with [name] [name] (postdoctoral fellow).

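### The SDQ's six-month recall is longer than the 77 days between pre and post surveys, so its pre-post change does not isolate change during the intervention

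*Combined protocol and SAP*

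**What the plan says.** The Synopsis names the SDQ among the supportive mental-health variables for the secondary objective: "Strengths and Difficulties Questionnaire (SDQ), WHO-5 Well-Being Index". Section 4.2.2 gives its recall period: "Participants are asked to rate whether each item is not true, somewhat true, or certainly true for them over the past six months". The Visit Schedule in section 6.1 has child and parent complete it at pre-intervention (Day 14 ± 7) and post-intervention (Day 91 ± 21). Session 1 is on Day 28 ± 7. Sections 4 and 6.1 add that the post survey opens after the last session and stays open for three weeks.

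Section 7.2.1 plans to examine change on the questionnaires that address the secondary objective, with paired t-tests of pre against post as the example. It names no measure.

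Section 4.2.2 describes CRAFFT 2.1 as asking for the number of days of "alcohol, marijuana, and other substance use in the past year". Section 4.2 lists it at pre-intervention ("WHO-5 Well-Being Index, CRAFFT 2.1, Autism Quotient-10 (AQ-10") and at post-intervention ("WHO-5 Well-Being Index, CRAFFT 2.1"). The Synopsis does not list it among the secondary variables.

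Two other mental-health measures have short recall. The WHO-5 asks how well each item "applies to them over the past 14 days", and the DSI-SS "assesses the frequency and intensity of suicidality in the past two weeks".

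**The concern.** The secondary objective asks whether symptoms fall while youth are in the program. A pre-post difference answers that only if the post score describes a period after the program began and the pre score a period before it. With six-month recall and 77 days between surveys, most of the period covered by the post answer lies before Session 1, and more than half of it was already covered by the pre answer.

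Sections 3.1 and 7.1 say the pilot data will inform effect sizes and the sample size of a future trial. If the SDQ change were used in that way, it would carry a distortion of unknown size. Nothing in the supplied text shortens the recall at post-intervention or mentions the overlap. Section 4.2.2 does consider sensitivity to change for another measure: the AQ-10 is not repeated because no change is expected.

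**Working it through.** The plan gives no overlap figure to reproduce. What follows is date arithmetic on the Visit Schedule.

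**Inputs.** Pre Day 14 (7 to 21), Session 1 Day 28 (21 to 35) and post Day 91 (70 to 112), all from section 6.1. Recall window W: SDQ six months, taken as 182.6 days; CRAFFT use frequency one year, 365 days (section 4.2.2).

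**Formulas.** Overlap = (W − (post − pre)) / W. Share of post window before Session 1 = (W − (post − Session 1)) / W.

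| | SDQ | CRAFFT use frequency |
|---|---|---|
| Overlap, nominal gap 91 − 14 = 77 | 105.6/182.6 = 58% | 288/365 = 79% |
| Overlap, shortest gap 70 − 21 = 49 | 133.6/182.6 = 73% | 316/365 = 87% |
| Overlap, longest gap 112 − 7 = 105 | 77.6/182.6 = 42% | 260/365 = 71% |
| Before Session 1, post on Day 91 (63 days later) | 119.6/182.6 = 65% | 302/365 = 83% |
| Before Session 1, post on Day 112 (84 days later) | 98.6/182.6 = 54% | 281/365 = 77% |

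The WHO-5 and DSI-SS windows are 14 days, shorter than both the 77-day and the 63-day gap. They do not overlap, and their post windows lie wholly after Session 1.

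**How much of an effect the SDQ would show.** Assume symptoms are stable up to Session 1 and then fall in one step, and that answers follow the stated recall.

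- Even weighting of the six months: 63/182.6 = 35% at Day 91; 84/182.6 = 46% at Day 112.
- Recency weighting with a 30-day half-life: (1 − 2^(−63/30)) / (1 − 2^(−182.6/30)) = 0.767/0.985 = 78% at Day 91. The same formula with 84 days gives 87%.
- Even weighting, with the effect building linearly over the 63 days: 31.5/182.6 = 17% of the final effect at Day 91.

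A steady decline at one slope before and after entry would show in full (100%). The documents do not say which history or weighting applies.

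**Check of a 30-day recall.** The shortest permitted pre-post gap is 49 days and the shortest gap from Session 1 to post is 70 − 35 = 35 days. Both exceed 30. So the two windows never overlap and the post window always falls after Session 1. With linear build-up and post on Day 91, the window runs from Day 61 to Day 91. The effect is 33/63 complete at its start and complete at its end, so even weighting shows (33/63 + 1)/2 = 76%, against 17% with six-month recall.

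**The case against.** The strongest reply is that the SDQ is a three-category global rating, not a day count, and youth may answer mainly from recent weeks. That stands, and it is why the size of the loss is left open.

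It also limits two stronger readings that a reader might infer.

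- **Exact cancellation.** One might say that the shared days cancel, so that SDQ change compares Day 14 to 91 with a block from about Day −169 to −92, before screening. That needs near-even weighting. Under even weighting 77/182.6 = 42% of the pre score's weight sits in that old block; with a 30-day half-life it is only 7%.
- **Reversed sign.** Suppose symptoms rose by the full size of the later effect over the 30 to 90 days before Day 1, then dropped at Session 1. Even weighting gives 0.422 × (1 − 63/77) = +0.08 of the effect, the wrong direction. With half-lives of 30, 60 and 90 days the change is −0.33 to −0.52, −0.10 to −0.23 and −0.03 to −0.12, all in the right direction. The entry rule ("mental health symptoms on the RCADS-P or -C with a T-score of 65 or more") makes a recent rise possible but does not show one. It also selects on anxiety and depression, which most SDQ subscales do not measure.

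Four further objections hold in part. A CRAFFT change test is an inference: substance use appears in neither the objectives nor the hypothesis, and the recall period of the CRAFFT risk-behavior items is not stated. No passage says that the SDQ in particular will size a future trial. Section 3.2 does not necessarily expect significant changes, and section 7.7 calls the analyses primarily descriptive. The administered wording is in the Measures Packet, which is not among the supplied documents. None of these removes the mismatch between the stated recall and the survey interval.

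**Conclusion.** The point holds for the SDQ, as a minor one. As described, its pre and post windows overlap by 58% on nominal days and by at least 42% on any permitted days. About 65% of the post window precedes Session 1. Its pre-post change therefore does not isolate change during the intervention. The share of a true step effect that would show at Day 91 runs from about 35% (even weighting) to about 78% (30-day half-life) if symptoms were stable beforehand. Other histories give other answers.

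This rests on the recall period in section 4.2.2 being the one administered at both surveys. It does not support a claim that the pilot will understate benefit: no direction of net bias can be derived, and the effect on standardized change is unknown because the SD of change may shrink as well. For CRAFFT use frequency the point is conditional on its change being tested. Nor does it undermine the secondary objective as a whole: the main outcomes, including the RCADS, are not affected, and neither are the WHO-5 and DSI-SS.

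**What to change.** Check the Measures Packet first. If it already shortens the recall, nothing further is needed. If not:

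1. For any group whose pre survey has not been answered, use one short recall period, identical at pre and post. Thirty days is an example that works across all permitted visit windows. Apply the same to CRAFFT use frequency if its change is to be examined.
2. For a group already surveyed with the long recall, keep the wording at post. Report SDQ (and CRAFFT use frequency) descriptively, with one sentence on recall length. Do not pool these data with those of a short-recall group, and do not use their change as an effect size for a future trial.

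The cost is a wording change in one survey, or one caveat sentence and a lighter analysis of supportive measures. The downsides are a departure from the standard wording, and change data on these measures from only about 10 youth if the first group has already answered its pre survey, or from none if both groups have.

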5.1 Study Population

The study population will consist of participants with internalizing disorders of mild to moderate severity who identify as LGBTQ, are 12-17 years of age, are fluent in English, and who live in New York, New Jersey, or Connecticut. Parents/legal guardians of these youth will also participate in pre-intervention and post-intervention assessments.

This intervention, and the treatments on which this intervention is based, was developed for the treatment of internalizing disorders, and thus eligible participants must meet criteria for anxiety, depression, or another internalizing disorder. Participants with severe internalizing disorders will be provided with referral information and excluded due to safety concerns and the need for more intensive intervention services.

This age group was selected due to the lack of interventions that have been adapted and tested for LGBTQ youth in adolescence, particularly in the 12-14 years age group. Moreover, this is a period during which internalizing psychopathology may emerge, making youth in this age range important targets for intervention.

These three US states were selected to allow for regional and geographic similarities between participants' locations (and thus potentially increase group rapport), to facilitate logistical aspects of the study (e.g., same time zone for all participants), and to aid in risk mitigation as needed, given the clinical nature of the sample (i.e., team has greater familiarity with local emergency services in these states). This geographic restriction might limit the generalizability of this intervention to LGBTQ adolescents in other parts of the US and world; however, as the goal of this pilot is to examine the feasibility and acceptability of the intervention in a small sample of diverse LGBTQ youth, we believe that this geographic restriction allows for diversity in participants while also limiting logistical barriers and mitigating risk.

5.2 Number of Participants

A total of 20 LGBTQ youth (aged 12-17 years) and their parents will be selected to participate in this study.

Given the numerous inclusion criteria, we anticipate needing to screen up to 100 participants in order to reach our target enrollment.

5.3 Eligibility Criteria

In order to be eligible for inclusion in the study, an individual must meet all of the following criteria:

- 12-17 years old
- Self-identify as LGBTQ (any diverse sexual orientation and/or gender identity)
- Live in New York, New Jersey, or Connecticut
- Fluent in English

- Meet diagnostic criteria for a DSM-5 internalizing disorder (any depressive, anxiety, obsessive-compulsive, or adjustment disorder)
- Have consistent, weekly access to an Internet-enabled electronic device that allows for video-conferencing
- Availability to attend 10 weekly 90 minute intervention sessions in summer 2021
- Access to a quiet, private place for intervention sessions
- Provision of informed consent from parent/guardian and assent from the youth

Any individual who meets any of the following criteria will be excluded from participation in this study:

- Evidence of any psychotic or bipolar spectrum diagnosis
- Active suicidality and/or homicidality (defined as active intent or concrete plan, as opposed to passive ideation) or psychiatric hospitalization within the past 6 months
- Significant cognitive impairment (as determined by an intellectual disability screener [CAIDS-Q]) or significant developmental disorder (if impairing youth's ability to participate in group therapy)
- Significant behavior disorder (e.g., oppositional defiant disorder, conduct disorder) if impairing youth's ability to participate in group therapy
- Received any cognitive-behavioral therapy treatment in the past 12 months
- Unstable psychotropic medications (defined as changes to antidepressant dosage in the past 3 months, or changes to a benzodiazepine dosage in the past month)

The virtual group sessions will exclude non-English speaking participants due to the need for participants to understand both the group facilitator and each other. As existing research highlights transportation as a key barrier to accessing services for economically disadvantaged LGBTQ youth (Zullo, [name], et al., 2021), the virtual format of the sessions could make the study more accessible to these youth. However, as participants will require a video-conferencing capable electronic device in order to participant, some economically disadvantaged potential participants will be excluded. Future trials might consider the addition of video-enabled e-tablets for youth and families without access.

